6.2.9. Day 8 or Discharge (± 24 Hours)

If the subject was discharged on Day 4 then follow directives in [Section 6.2.8](#) and do not have subject return for a Day 8 visit. Sponsor and investigator documentation of TIEs must occur at Day 8. A telephone follow-up on Day 8 for collection of serious adverse events and adverse events since discharge will be completed if the subject is discharged prior to Day 8. If the subject was not discharged on Day 4, the following procedures will be completed on the day the subject is discharged (Day 5, Day 6, Day 7, or Day 8) or Day 8 if the subject remains in the hospital longer than Day 8:

- Complete comprehensive physical examination: physical examination should consist of assessments of general appearance, HEENT, skin, heart (auscultation), lungs (auscultation), abdomen (palpitation and auscultation), and extremities with attention to swelling, general or localized tenderness, entire leg or calf swelling, edema, and collateral superficial veins.
- Collect vital signs: including temperature, blood pressure, pulse rate, and respiratory rate (supine).
- The highest observed blood pressure result for each of the following Day 1 post-dose time intervals is to be collected: Hour 0-3, Hour 3-6, Hour 6-12, and Hour 12-24 for a total of 4 documented highest observed BP results (based on systolic blood pressure).
- Collect ECG: single standard supine 12-lead ECG will be collected.

- Collect the following blood samples:
 - Safety:
 - D-dimer sample collection to be processed at **local** laboratory.
 - Immunogenicity sample collections (ADA, NAb, FX activity).
- Collect urine sample for urinalysis for shipment to a central laboratory.
- Complete Thrombosis Clinical Probability Scores.
 - Review Wells' algorithm ([Appendix 2](#)).¹⁵ If indicated, obtain lower extremity Doppler Ultrasonography and/or pulmonary imaging study; no nicotine intake should occur for approximately 1 hour prior to testing.
- Discuss birth control protocol specifications to male subjects who are able to father children and are sexually active and at risk of pregnancy-see [Section 4.4](#). This is to be documented in the subject's chart.
- Secure approval for release of health care information from study subject/legal guardian/legally acceptable representative as permitted by local, state, and institutional guidance to assist with collection of adverse events through Day 8 (if discharged prior to Day 8) and collection of serious adverse events through Day 43.
- Monitoring of serious adverse events and adverse events. Telephone follow-up call on Day 8 for collection of serious adverse events and adverse events if subject was discharged prior to Day 8.
- Monitoring of concomitant medications and treatments.
- Collect appropriate health resource utilization information which includes: admission date of subject to the stroke unit/ICU, discharge date of the subject from the stroke unit/ICU, admission/discharge date from the hospital (if moved from stroke unit/ICU) and as applicable, date subject began in-patient rehabilitation, and discharge date subject completed in-patient rehabilitation.

6.3. Follow-up Visits

A study site should make every effort to have the subject attend the follow-up office/clinic visits, including arranging transportation if feasible (Day 43 and Day 91). If a subject is unable to attend the Day 43 and/or Day 91 study visit, or attend a scheduled remote visit on these days, a telephone follow-up for collection of serious adverse events since the last visit should occur if permitted per local, state, and institutional guidance.

6.3.1. Day 43 (±7 Days)

The following procedures will be completed:

- Collect the following blood samples:
 - Immunogenicity sample collections (ADA, NAb, FX activity, Anti-CHO and Anti-PACE) for shipment to a central laboratory.
- Conduct the mRS.
- Conduct the NIHSS.
- Document birth control utilized through the protocol required 28 days after the single dose of investigational product for male subjects who are able to father children and are sexually active and at risk of pregnancy, see [Section 4.4](#).
- Monitoring of serious adverse events.
- Monitoring of concomitant medications and treatments.
- Collect appropriate health resource utilization information which includes: as applicable, date subject began in-patient rehabilitation, discharge date subject completed in-patient rehabilitation, date subject began out-patient rehabilitation, and discharge date subject completed out-patient rehabilitation.

6.3.2. Day 91 (±7 Days)

The following procedures will be completed:

- Collect the following blood samples **only** if subject tested positive for antibody immune response to PF-05230907 at Day 43 (sites will be notified if a subject has evidence of a previous antibody immune response to PF-05230907):
 - Immunogenicity sample collections (ADA, NAb, and FX activity) for shipment to a central laboratory.
- Conduct the mRS.
- Conduct the NIHSS.
- Collect appropriate health resource utilization information which includes: as applicable, date subject began out-patient rehabilitation, and discharge date subject completed out-patient rehabilitation.

6.4. Subject Withdrawal

Withdrawal of consent: Subjects who request to discontinue study treatment will remain in the study and must continue to be followed for protocol specified follow-up procedures. The only exception to this is when a subject specifically withdraws consent for any further contact with him or her or persons previously authorized by the subject to provide this information. Subjects should notify the investigator in writing of the decision to withdraw consent from future follow-up, whenever possible. The withdrawal of consent should be explained in detail in the medical records by the investigator and entered on the appropriate case report form (CRF) page. In the event that vital status (whether the subject is alive or dead) is being measured, publicly available information should be used to determine vital status only as appropriately directed in accordance with local law.

Lost to follow-up: All reasonable efforts must be made to locate subjects to determine and report their ongoing status. This includes follow-up with persons authorized by the subject as noted above. Lost to follow-up is defined by the inability to reach the subject after a minimum of 2 documented phone calls, faxes, or e-mails as well as lack of response by the subject to 1 registered mail letter. All attempts to contact the subject and information received during contact attempts should be documented in the subject's medical records. If it is determined that the subject has died, the site will use permissible local methods to obtain the date and cause of death. If the investigator's use of a third-party representative to assist in the follow-up portion of the study has been included in the subject's informed consent, then the investigator may use a sponsor-retained third-party representative to assist site staff with obtaining the subject's contact information or other public vital status data necessary to complete the follow-up portion of the study. The site staff and representative will consult publicly available sources, such as public health registries and databases, in order to obtain updated contact information. If, after all attempts, the subject remains lost to follow-up, then the last-known-alive date as determined by the investigator should be reported and documented in the subject's medical records.

Subjects may withdraw from the study at any time at their own request, or they may be withdrawn at any time at the discretion of the investigator or sponsor for safety or behavioral reasons, or the inability of the subject to comply with the protocol-required schedule of study visits or procedures at a given study site.

If a subject does not return for a scheduled visit, every effort should be made to contact the subject. All attempts to contact the subject and information received during contact attempts must be documented in the subject's medical record. In any circumstance, every effort should be made to document subject outcome, if possible. The investigator should inquire about the reason for withdrawal, request that the subject return for a final early withdrawal visit, if applicable, and follow up with the subject regarding any unresolved adverse events (AEs).

If a subject is homebound or in a rehabilitation facility and unable to attend the Day 43 and/or Day 91 visit, a study site should make every effort to assist the subject with attending an office/clinic visit (eg, arrange transportation) within the protocol window time period if at all possible as indicated in [Section 6.3.1](#). If the subject is unable to attend a study withdrawal

visit, or is unable to attend a scheduled remote study withdrawal visit, a telephone follow-up for collection of all adverse events since the last visit should occur if permitted per local, state, and institutional guidance.

If a subject withdraws prior to Day 8/discharge, the following assessments should be completed:

- The highest observed blood pressure result (based on systolic blood pressure) for each of the following Day 1 post-dose time intervals is to be collected: Hour 0-3, Hour 3-6, Hour 6-12, and Hour 12-24 for a total of 4 documented highest observed BP results.
- Monitoring of serious adverse events.
- Monitoring of adverse events.
- Monitoring of concomitant medications and treatments.
- Collect appropriate health resource utilization information which includes: admission date of subject to the stroke unit/ICU, discharge date of the subject from the stroke unit/ICU, admission/discharge date from the hospital (if moved from stroke unit/ICU) and as applicable, date subject began in-patient rehabilitation, and discharge date subject completed in-patient rehabilitation.

If a subject withdraws after Day 8/discharge and prior to Day 43 or if antibody results at Day 43 are not yet available, the following assessments should be completed:

- Collect the following blood samples:
 - Immunogenicity sample collection (ADA, NAb, and FX activity) for shipment to a central vendor.
- Conduct the mRS.
- Conduct the NIHSS.
- Document birth control utilized through the protocol required 28 days after the single dose of investigational product for male subjects who are able to father children and are sexually active and at risk of pregnancy, see [Section 4.4](#).
- Monitoring of concomitant medications and treatments.
- Monitoring of serious adverse events.
- Collect appropriate health resource utilization information which includes: as applicable, date subject began out-patient rehabilitation and discharge date subject completed out-patient rehabilitation.

If a subject withdraws after Day 43 and prior to Day 91, the following assessments should be completed:

- Collect the following blood samples **only** if subject tested positive for antibody immune response to PF-05230907 at Day 43 (sites will be notified if a subject has evidence of a previous antibody immune response to PF-05230907):
 - Immunogenicity sample collections (ADA, NAb, and FX activity) for shipment to a central vendor.
- Conduct the mRS.
- Conduct the NIHSS.
- Collect appropriate health resource utilization information which includes: as applicable, date subject began out-patient rehabilitation and discharge date subject completed out-patient rehabilitation.

If the subject withdraws from the study, and also withdraws consent for disclosure of future information, no further evaluations should be performed, and no additional data should be collected. The sponsor may retain and continue to use any data collected before such withdrawal of consent.

7. ASSESSMENTS

Investigational sites are encouraged to explore the option for remote visits at the subject's point-of-care as an alternative mechanism to conduct the study specified visits.

Every effort should be made to ensure that the protocol-required tests and procedures are completed as described. However, it is anticipated that from time to time there may be circumstances, outside of the control of the investigator that may make it unfeasible to perform the test. In these cases the investigator will take all steps necessary to ensure the safety and well-being of the subject. When a protocol-required test cannot be performed, the investigator will document the reason for this and any corrective and preventive actions that he or she has taken to ensure that normal processes are adhered to as soon as possible. The study team will be informed of these incidents in a timely fashion.

7.1. Safety Assessments

Safety will be assessed by physical examinations, vital signs, ECGs, clinical safety laboratory results, Thrombosis Clinical Probability Scores, CT or MR scan of the brain at 72 hours, Doppler ultrasonography of the lower extremities at 72 hours (and discharge/Day 8 if applicable), and spontaneous reporting of SAEs and AEs including TIEs in all subjects who receive at least one dose of study drug.

Unscheduled safety assessments may be performed at any time during the study to assess any perceived safety concerns. Investigators and Pfizer Clinicians (or designees) will review individual subject data throughout the conduct of the study and the eDMC will be responsible for ongoing monitoring of study safety data (see [Section 9.8](#)).

7.1.1. Physical Examination

Physical examinations may be conducted by a physician, trained physician's assistant, or nurse practitioner as acceptable according to local regulation. Comprehensive physical examinations and targeted physical examinations are performed at the visits specified in the [Schedule of Activities](#). Clinically significant abnormalities that represent a change from the most recent prior observation should be considered for recording as AEs.

7.1.1.1. Comprehensive Physical Examination

A comprehensive physical examination will include the following parameters and body systems: general appearance, HEENT, skin, heart (auscultation), lungs (auscultation), abdomen (palpitation and auscultation) and extremities with attention to swelling, general or localized tenderness, entire leg or calf swelling, edema, and collateral superficial veins.

7.1.1.2. Targeted Physical Examination

A targeted physical examination will include the following parameters and body systems: general appearance, skin, heart (auscultation), lungs (auscultation), abdomen (palpitation and auscultation), and extremities with attention to swelling, general or localized tenderness, entire leg or calf swelling, edema, and collateral superficial veins.

7.1.1.3. Weight and Height

Actual weight should be measured in kilograms (kg). If actual weight cannot be obtained at screening, then subject reported weight from within the last 3 months may be utilized and actual weight should be collected as soon as possible post-dose. Subject reported height is acceptable.

7.1.2. Vital Signs

Vitals signs including temperature, blood pressure, pulse rate, and respiratory rate (supine) will be measured at the visits specified in the [Schedule of Activities](#). Clinically significant abnormalities that represent a change from the most recent prior observation should be considered for recording as AEs. If during hospital confinement period, the magnitude of a vital sign abnormality is sufficient to be reported as an AE, then vital signs should be collected as a daily unscheduled observation during the hospital confinement period (eg, Day 5 through Day 8/discharge) and should be followed until the AE resolves or stabilizes (see [Section 8.1](#)).

- Body temperature should be measured by oral, tympanic, axillary or temporal method. The method chosen should be used consistently throughout the study.

- Supine blood pressure (BP) measurement should be measured with the subject's arm supported at the level of the heart and recorded to the nearest mm Hg after 5 minutes of rest whenever possible and as permitted by the subject's medical condition. Blood pressure should not be taken from the arm with an intravenous infusion. The same arm (preferably the dominant arm) should be used throughout the study. A properly sized and calibrated blood pressure cuff will be used to measure blood pressure each time. The use of an automated device for measuring BP and pulse rate is acceptable, although, when done manually, pulse rate will be measured in the brachial/radial artery for at least 30 seconds. When the timing of these measurements coincides with a blood collection, blood pressure and pulse rate should be obtained prior to the nominal time of the blood collection.
- Respiratory rate (RR) should be measured after 5 minutes rest in supine position by observing and counting the respirations of the subject for 30 seconds and multiplied by 2. The use of an automated device for measuring RR is acceptable. When blood pressure is to be taken at the same time, respiration measurement should start after 5 minutes of rest and before blood pressure measurement.

7.1.2.1. Highest Observed Blood Pressure Documentation

The highest observed blood pressure (systolic pressure) result reflected in the hospital record/source documents will be recorded for the time-intervals specified in the [Schedule of Activities](#).

7.1.3. ECG

A single standard supine 12-lead ECG should be performed after the subject has rested quietly for at least 10 minutes in a supine position at times specified in the [Schedule of Activities](#). Clinically significant abnormalities that represent a change from the Day 1 screening/baseline visit should be considered for recording as AEs and evaluated further as clinically warranted.

The Day 1 screening ECG values will serve as each subject's baseline values. When the timing of the measurements coincides with a blood collection, the ECG should be obtained prior to the nominal time of the blood collection. To ensure safety of the subjects, a qualified individual (eg, investigator, sub-investigator) at the study site will make comparisons to baseline measurements. A paper or digital copy of the ECG should be filed in the subjects chart and must be available to the sponsor upon request.

If a scheduled single ECG assessment reveals a clinically significant abnormality (other than the Day 1 screening value) then 2 additional ECGs should be collected to confirm the original observation.

7.1.4. Thrombosis Clinical Probability Scores

Thrombosis clinical probability scores consist of two assessments, the Simplified Clinical Model for Assessment of deep vein thrombosis (DVT) and Variables Used to Determine Patient Pretest Probability for Pulmonary Embolism (PE). These assessments are used to

categorize subjects as having low, moderate or high probability of having a DVT or PE respectfully. A physician, trained physician's assistant, or nurse practitioner as acceptable according to local regulation will complete each assessment by reviewing the clinical variables and indicating the corresponding score. These scores are totaled and compared with the coordinating probability score located in the footnote of each assessment scale.

The Probability Scores will be completed and calculated at times specified in the [Schedule of Activities](#). Sites should refer to Well's publication "Integrated strategies for the diagnosis of venous thromboembolism" for additional guidance regarding recommended post treatment evaluation for possible deep vein thrombosis and/or pulmonary embolism, which may require additional Doppler lower extremity ultrasonography.¹⁵

7.1.5. Doppler Lower Extremity Ultrasonography

A Doppler lower extremity ultrasonography will be completed at the time specified in the [Schedule of Activities](#). In the event of abnormal Doppler lower extremity ultrasonography result, the investigator should initiate treatment and/or additional diagnostic studies as clinically warranted. No nicotine intake should occur for approximately 1 hour prior to testing.

7.1.6. Cardiac Troponin I

Serial results of cardiac troponin I should be followed in conjunction with other correlated parameters including ECG in order to assess for the possibility of acute evolving or recent MI based on criteria from Myocardial infarction redefined – A consensus document of The Joint European Society of Cardiology/American College of Cardiology Committee for the redefinition of myocardial infarction.²⁰ For safety analyses the central laboratory results for cardiac troponin I will take precedence over local determinations for cardiac troponin T.

7.1.7. CT or MR Scan at Day 4 (72 Hours Post-dose)

A CT or MR scan will be completed as indicated in the [Schedule of Activities](#) and reviewed locally by a qualified physician for evidence of a treatment emergent ischemic event at Day 4 (72 hours post-dose). CT scan is the preferred imaging modality however for the Day 4 assessment a site may substitute an MR scan based on local standard of care (SoC), local regulatory, or clinical considerations at the investigator's discretion. Clinically significant results that represent changes from the Day 2 (24 hour post-dose) imaging should be considered for recording as AEs or SAEs per protocol [Section 8](#). The scan will be sent to central vendor for final analysis.

7.1.8. TIEs Through Day 8

TIEs ([Appendix 1](#)) are to be reported by the study site following protocol [Section 8.6.1](#) and [Section 8.14](#). The dose toxicity relationship for each cohort is based upon the TIE data and is reviewed as part of the mCRM design, therefore it is essential these events be reported as AEs or SAEs in a timely manner by the study site.

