4.1. Inclusion Criteria

Subject eligibility should be reviewed and documented by an appropriate member of the investigator's study team before subjects are included in the study.

Subjects must meet all of the following inclusion criteria to be eligible for enrollment into the study:

1. Evidence of a personally signed and dated informed consent document indicating that the subject (or a legally acceptable representative/legal guardian, in countries where it is accepted) has been informed of all pertinent aspects of the study.

For sites in Sweden, only subjects that comply with the criteria specified in [Appendix 8](#) may consent for the study.

2. Reasonable likelihood subject will comply with scheduled visits, laboratory tests, and other study procedures.
3. Male and/or female subjects (female subjects must be of non-child bearing potential) between the ages of 18 and 79 years of age.

Female subjects who are of non-childbearing potential are defined as meeting at least 1 of the following criteria:

- Have undergone a documented hysterectomy and/or bilateral oophorectomy;
- Have medically confirmed ovarian failure; or
- Achieved postmenopausal status, defined as follows: cessation of regular menses for at least 12 consecutive months with no alternative pathological or physiological cause.

All other female subjects (including females with tubal ligations) are considered to be of childbearing potential.

4. ICH as documented by CT scan within 6.0 hours of symptom onset.
5. Baseline ICH volume >5 mL and <60 mL based on the ABC/2 method (see [Appendix 3](#)).
6. At the time of treatment allocation, capability to treat with investigational product within 6.0 hours of symptom onset.
7. Body Mass Index (BMI) must be ≤ 40 kg/m².

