Cardiac troponin I increased	3	1: Levels above the upper limit of normal and below the level of myocardial infarction as defined by the manufacturer 2: Not defined 3: Levels consistent with myocardial infarction as defined by the manufacturer 4: Not defined 5: Not defined
Ischemia cerebrovascular	1 or higher and associated with lesion(s) on CT/MRI not contiguous with the ICH lesion and in a discrete separate area of the brain	1: Asymptomatic; clinical or diagnostic observations only; intervention not indicated 2: Moderate symptoms 3: Not defined 4: Not defined 5: Not defined

Adverse Event	Grade Defining a TIE	Grade and Description
Portal vein thrombosis	2 or higher	1: Not defined 2: Intervention not indicated 3: Medical intervention indicated 4: Life-threatening consequences; urgent intervention indicated 5: Death
Ischemic stroke based upon CTCAE V4.03 toxicity criteria for stroke	1 or higher and associated with lesion(s) on CT/MRI not contiguous with the ICH lesion and in a discrete separate area of the brain	1: Asymptomatic or mild neurologic deficit; radiographic findings only 2: Moderate neurologic deficit 3: Severe neurologic deficit 4: Life-threatening consequences; urgent intervention indicated 5: Death

Adverse Event	Grade Defining a TIE	Grade and Description
Transient Ischemic attacks	2	1: Mild neurological deficit with or without imaging confirmation 2: Moderate neurologic deficit with or without imaging confirmation 3: Not defined 4: Not defined 5: Not defined
Purpura	2 or higher	1: Combined area of lesions covering <10% BSA 2: Combined areas of lesions covering 10-30% BSA; bleeding with trauma 3: Combined areas of lesions covering >30% BSA; spontaneous bleeding 4: Not defined 5: Not defined

Adverse Event	Grade Defining a TIE	Grade and Description
Superior vena cava syndrome	1 or higher	1. Asymptomatic; incidental finding of SVC thrombosis 2. Symptomatic; medical intervention indicated (eg, anticoagulation, radiation, or chemotherapy) 3: Severe symptoms; multi-modality intervention indicated (eg, anticoagulation, chemotherapy, radiation, stenting) 4: Life-threatening consequences; urgent multi-modality intervention indicated (eg, lysis, thrombectomy, surgery) 5: Death

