#### **6.6.6.2. Brain Imaging Study and Doppler Ultrasound**

A CT or MR scan will be completed as indicated in the SoA of the protocol and reviewed locally by a qualified physician for evidence of a treatment emergent ischemic event. Doppler ultrasonography of the lower extremities will be conducted at screening and at 72 hours post-dose (and discharge/Day 8 if applicable). Listing of Brain imaging study [CT  $\pm$  MRI] scan results, and Doppler ultrasound of the lower extremity will be generated by dose group. New onset (ie, absent at baseline, present at 72 hours) ischemic findings not contiguous with the area of hemorrhage will be summarized. Treatment emergent abnormal Doppler ultrasound results will be listed and summarized.

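### Silent cerebral lesions feed the mCRM, but the Day 4 scan may be MR against earlier CT, no analysis tests this, and Protocol 7.1.7 uses a different reference scan from the SAP imaging summaries

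*Protocol*

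**What the plan says.** **Silent lesions count.** In Appendix 1 of the Protocol, repeated in the SAP, cerebrovascular ischemia and ischemic stroke are TIEs at grade "1 or higher and associated with lesion(s) on CT/MRI not contiguous with the ICH lesion and in a discrete separate area of the brain". Grade 1 is described as "1: Asymptomatic; clinical or diagnostic observations only; intervention not indicated" for the former and "1: Asymptomatic or mild neurologic deficit; radiographic findings only" for the latter. A TIE of this kind can rest on imaging alone.

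**Modality.** Eligibility requires "ICH as documented by CT scan within 6.0 hours of symptom onset" (Protocol 4.1), and the Day 2 scan is also CT (Protocol 6.2.6). For Day 4, CT is preferred, but "a site may substitute an MR scan based on local standard of care (SoC"), or for regulatory or clinical reasons, as the investigator decides (Protocol 7.1.7).

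**Reference scan.** Protocol 7.1.7: "Clinically significant results that represent changes from the Day 2 (24 hour post-dose) imaging should be considered for recording as AEs" or SAEs. SAP 6.6.6.2: "New onset (ie, absent at baseline, present at 72 hours) ischemic findings not contiguous with the area of hemorrhage will be summarized". SAP 6.3.1.2 words its CT summary the same way.

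**TIE rule.** SAP 3.1.1 requires onset or worsening after dosing and by Day 8. It names neither a reference scan nor a modality.

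**Sensitivity analyses.** SAP 4.2.1, 6.1.1.1 and 6.5.3 cover replaced subjects and the dose actually given. None concerns imaging.

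**The concern.** The mCRM takes a yes/no TIE for each subject, and at Grade 1 that answer can depend on what a scan shows and what it is compared with. When the Day 4 scan is MR and the earlier scans are CT, a lesion that appears for the first time on Day 4 may be a new event or may reflect the change of instrument. Neither document says how to judge this or plans to examine it.

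The reference scan matters for a related reason. The Day 2 scan is taken after dosing. The half-life reported in Protocol 1.3.2 is about 4 minutes (4.6 at 3 µg/kg and 3.7 at 5 µg/kg), so the first 24 hours are part of the period of interest. A prompt tied to change since Day 2 leaves out lesions that arose in that period and then stayed stable.

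At stake is whether the estimated MTD rests on lesions whose classification depends on the scanner, and whether the report could list new-onset lesions that the model never received.

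**Working it through.** **1. Passages side by side.** Consider a separate lesion that is absent at baseline, visible on Day 2 and unchanged on Day 4.

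| Text | Treatment of this lesion |
|---|---|
| Protocol 7.1.7, recording prompt | No change from Day 2, so not prompted |
| SAP 6.3.1.2 and 6.6.6.2, imaging summaries | New onset |
| SAP 3.1.1, TIE rule | Qualifies if onset was after dosing; no reference scan named |
| Protocol 7.1.8, 8.2 and 6.2.9 | Sites report TIEs; AEs are recorded from dosing to Day 8; TIEs are documented at Day 8 |

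The last row can still capture the lesion. However, Protocol 6.2.6 only sends the Day 2 CT to the central vendor. A local read for ischemia is specified for Day 4 alone (6.2.8, 7.1.7).

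**2. Reproducing the plan's model.** With β = 1, p = (1 + tanh x)/2, so x = atanh(2p − 1). At 5 µg/kg, p = 0.08 gives atanh(−0.84) = −1.22. All 15 adjusted doses in Table 3 match to two decimals.

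**3. Effect of one added TIE.** Inputs are the Table 3 rates pᵢ, the Unif[0,3] prior on β, the 15% target, cohorts of 3 and the cap of two dose levels (SAP 2.2, 5.2.2 and 5.2.3). The fitted rate at dose i is pᵢ^β̂, where β̂ is the posterior mean. The posterior is proportional to the product over subjects of pᵢ^β for a TIE and (1 − pᵢ^β) otherwise, integrated numerically in place of MCMC. The model MTD is the highest grid dose with fitted rate below 0.15. The next dose also obeys the cap.

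| Data | β̂ | Model MTD | Next dose (µg/kg) |
|---|---|---|---|
| 0/3 at 5 | 1.82 | 19 | 8 (capped) |
| 1/3 at 5 | 0.72 | 4 | 4 |
| 0/3 at 5, 0/3 at 8 | 1.97 | 24 | 12 (capped) |
| 0/3 at 5, 1/3 at 8 | 1.13 | 10 | 10 |
| 0/3 at 5 and 8, 0/3 at 12 | 2.11 | 24 | 19 (capped) |
| 0/3 at 5 and 8, 1/3 at 12 | 1.52 | 15 | 15 |

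As a check on the first pair: 0.325^1.82 = 0.13 at 19 µg/kg and 0.38^1.82 = 0.17 at 24, so the model MTD is 19. With one TIE, 0.06^0.72 = 0.13 at 4 and 0.08^0.72 = 0.16 at 5, so it is 4.

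With 0/3 at each of 5, 8 and 12, and 12 subjects at 19, TIE counts of 1, 2 and 3 at 19 give β̂ = 2.24, 1.94 and 1.65, and model MTDs of 24, 19 and 15. These are illustrative end states, not a predicted allocation path.

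**4. Size of the modality effect.** The documents give no MR frequency and no CT/MR detection difference. As an assumption only, let MR add a silent-lesion rate a, independent of other TIEs, with every subject scanned by MR. Take the 5.5% background in Protocol 1.4, whose imaging method is not stated. The rate becomes 1 − 0.945 × (1 − a): 5.5%, 10.2%, 15.0% and 24.4% for a = 0, 5, 10 and 20%. Nothing in the documents says where in this range, if anywhere, the truth lies.

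**The case against.** The strongest reply is that most of the safeguards already exist. A reader might infer that the Protocol and SAP define the TIE itself against different scans. They do not: the SAP baseline wording governs descriptive imaging summaries, SAP 3.1.1 names no reference scan, and 7.1.7 is a recording prompt that follows the Protocol's habit of comparing with the most recent prior finding. A reader might also infer that a Day 2 lesion is lost. The documents do not support that either. AEs are recorded from dosing to Day 8, sites must report TIEs, TIEs are documented at Day 8, and the medical monitor and eDMC chair see brain imaging findings between cohorts (SAP 7.4.2). Protocol 7.1.7 also asks for a Day 4 read for treatment-emergent ischemia in general terms.

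On modality, the SAP separates pre-existing from new-onset ischemia in its imaging categories, so readers are expected to tell them apart. An imaging procedure manual (Protocol 7.7.1), not available here, may hold reading rules. Any single TIE, however it arises, moves a small mCRM in the way shown above.

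Much of this stands. It narrows the reference-scan problem to a mismatch between a site prompt and a summary, with no local Day 2 ischemia read specified. It also means the dose shifts measure sensitivity to one event, not the frequency of modality-driven events. It does not supply a rule in these documents for an MR finding against a CT reference, or any analysis that would show its influence.

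**Conclusion.** The point holds as a low-severity improvement. Silent lesions enter the mCRM, the Day 4 instrument can differ from the earlier ones, and no planned analysis shows whether the MTD depends on that. The Protocol prompt and the SAP summaries also need reconciling on the reference scan.

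The bias itself cannot be quantified, and the documents do not establish that there is one. What can be stated is leverage under the plan's own model: one added TIE changes the dose after cohort 1 from 8 to 4 µg/kg, and in the later cases checked moves the recommendation by one grid level (12 versus 10; 19 versus 15; and 24, 19, 15 for 1, 2, 3 TIEs among 12 subjects at 19). A reader might cite a fall from 19 to 4 after cohort 1; that is the uncapped model MTD, and the escalation cap makes the assigned doses 8 and 4. Nor can MR use be treated as varying only by site, because 7.1.7 also allows clinical reasons and investigator discretion, so it can vary by subject.

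These figures assume the Table 3 rates, the Unif[0,3] prior, posterior-mean estimation and no override by the sponsor or eDMC. Enrollment ended early after 21 subjects (SAP 1), so the remaining value lies mainly in the analysis and in documenting how TIEs were classified.

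**What to change.** - **Protocol 7.1.7:** reconcile it with SAP 6.3.1.2 and 6.6.6.2, so that a new ischemic lesion is judged against the pre-dose baseline scan.
- **SAP 6.1.1.1, listing:** give the modality of the scan behind each imaging-based TIE.
- **SAP 6.1.1.1, analysis:** add one sensitivity mCRM run that excludes asymptomatic lesions seen on MR and on no CT, and report it beside the main estimate.

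The baseline reference does not remove the modality question, because the baseline scan is also CT. The sensitivity run is what addresses it.

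The cost is one phrase in the Protocol, one listing column and one extra run. Some excluded lesions may be real drug effects, so the run should remain a sensitivity analysis. The choice of scan at a site, the TIE definition and dosing stay as they are.
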